8.7 Genetics

Genetics are not evaluated in this study.

8.8 Biomarkers

Biomarkers, other than the pharmacodynamic markers, are not evaluated in this study.

8.9 Medical Resource Utilization and Health Economics

Medical Resource Utilization and Health Economics parameters will not be evaluated in this study.

9.0 STATISTICAL CONSIDERATIONS

9.1 Statistical Hypotheses

The primary statistical hypothesis to be tested in this study is the hypothesis that the ATI-450 treatment group is superior to placebo for the treatment of HS based upon the 12-week change from Baseline in inflammatory nodules and abscesses versus the null hypothesis of no difference. This hypothesis will be conducted using a one-sided testing procedure with an alpha level of 0.05. No adjustment for multiplicity will be made.

Secondary superiority hypotheses will be tested on the secondary efficacy endpoints to gather supportive evidence for the primary hypothesis. These secondary assessments will have the same null and alternative hypotheses as the primary and will be tested using a one-sided procedure with an alpha level of 0.05.

9.2 Sample Size Determination

Ninety (90) randomized patients will provide 90.3% power to demonstrate the superiority of ATI-450 to placebo in the reduction in inflammatory nodules and abscesses at Week 12. This power computation assumes that the reduction in the placebo arm will be on average 2.5 nodules/abscesses and the ATI-450 reduction will be on average 4.75 nodules/abscesses. The assumed standard deviation for the number of nodules/abscesses was assumed to be 3.6. These

sample size assumptions were based on the values observed in the adalimumab PIONEER I and PIONEER II Phase 3 trials ([Frew et al, 2020](#)). The assumed reduction in nodules/abscesses for ATI-450 was chosen to be slightly less than that shown in the PIONEER I and PIONEER II Phase 3 in order to account for the potential impact of dropouts on the efficacy.

9.3 Populations for Analyses

For purposes of analysis, the analysis sets in [Table 4](#) are defined.

Table 4 Analysis Sets

Analysis Set	Description
Full Analysis Set (FAS)	All patients who have been randomized and administered at least 1 dose of study treatment. The efficacy analyses will be conducted on the FAS population as randomized.
Per Protocol (PP)	All randomized patients who remain on study treatment, complete their assessments for their Day 85 visit, with no major protocol violations.
Safety Analysis Set	All patients randomly assigned to study treatment and who take at least 1 dose of study treatment. Patients will be analyzed according to the treatment they actually received.
Pharmacokinetic (PK)	All patients randomly assigned to study treatment and who take at least 1 dose of study treatment and have at least 1 evaluable PK measurement
Pharmacodynamic (PD)	All patients randomly assigned to study treatment and who take at least 1 dose of study treatment and have at least 1 evaluable PD measurement

9.4 Statistical Analyses

Details of all statistical summaries will be provided in the study-specific SAP.

All data will be presented by treatment group. Descriptive statistics (number of observations, mean, standard deviation, median, minimum, and maximum) will be provided for continuous variables, and counts and percentages will be presented for categorical variables. Unless otherwise stated, hypothesis tests and corresponding *P* values will be 1-sided with an alpha level of 0.05. No adjustments will be made for multiplicity.

Baseline is defined as the last nonmissing measurement before, or on the date of first administration of study treatment.

9.4.1 Efficacy Analyses

Table 5 Efficacy Analyses

Endpoint	Statistical Analysis Methods
Primary	
All efficacy summaries will be conducted on both the FAS and PP populations.
 
The primary efficacy analysis will be the treatment comparison of the change from Baseline in inflammatory nodules and abscesses at Week 12 in the FAS population. This analysis will be conducted within the context of a Mixed Model Repeated Measures (MMRM). This model will include factors for treatment group, time, and time by treatment interaction as well as a Baseline covariate. Patient identifiers will be included in the model in a manner that allows observations within a given patient over time to be treated as repeated measures. Point estimates and 90% confidence intervals (CI) for the difference in least square means (LS means) will be provided in addition to the 1-sided P values.

Secondary	
Treatment comparisons for all secondary responder endpoints (percentage of patients meeting HiSCR at Week 12, percentage of patients achieving at least 30% reduction from Baseline in NRS30-PGA Skin Pain, and percentage of patients who experience at least a 25% increase in AN count with a minimum increase of 2 relative to Baseline over the 12-week treatment period) will be conducted using a logistic regression applied to each time point separately. The logistic regression will include a factor for treatment group and a covariate for Baseline, where appropriate. These analyses will be done for both the FAS and PP populations.
 
Treatment comparisons for all continuous secondary endpoints will be conducted using a MMRM like the 1 described for the primary endpoint. These analyses will be done for both the FAS and PP populations.

Exploratory	Will be described in the SAP finalized before database lock.

Abbreviations: AN=abscess and inflammatory nodule; FAS=Full Analysis Set; HiSCR=Hidradenitis Suppurativa Clinical Response; NRS30-PGA=Patient's Global Assessment; PP=Per Protocol; SAP=Statistical Analysis Plan.

9.4.2 Safety Analyses

The Safety population will be used for the analysis of safety data (AEs, exposure to study treatment, clinical laboratory values, vital signs, and ECG).

Adverse events will be coded with MedDRA and WHODrug Global B3 March 2021. The TEAEs are defined as AEs with an onset date on or after the date of first administration of study treatment and before the date of last administration of study treatment +30 days. Treatment-emergent adverse events will be presented by system organ class and preferred term in frequency tables. Patients with multiple AEs will be counted only once within each preferred term and system organ class. Key patient information for patients with an AE with an outcome of death, patients with SAEs, and patients with an AE leading to discontinuation of study treatment will be listed.

Laboratory data (hematology, serum chemistry, coagulation, and urinalysis) will be converted to Système International units for reporting and processing purposes. Absolute values and changes from Baseline will be presented descriptively. Laboratory data outside study specific reference ranges will be listed. Vital signs and ECG parameters will be presented descriptively.

9.4.3 Other Analyses

9.4.3.1 ATI-450 Drug Concentrations and Pharmacokinetic Analyses

All PK analyses will be performed using the PK Population. Plasma concentrations of ATI-450 and its primary circulating metabolite, CDD-2164, will be summarized by day and sample time. Concentration versus time since dose (Days 1, 8, 15, 29, 43, 57, and 85) will be displayed by linear scale. Population PK modeling and related exposure response modeling may be explored, as appropriate.

9.4.3.2 [REDACTED]

[REDACTED]

[REDACTED]

9.4.4 Missing Data

Missing data will not be imputed for the safety summaries, or the efficacy summaries conducted on the PP population. All efficacy analyses conducted on the FAS population will use a LOCF analysis. Additionally, a sensitivity analysis will be conducted for categorical endpoints conducted on the FAS using the non-responder imputation method. Further details regarding the imputation of data that are missing or following intercurrent events will be provided in the SAP.

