#### **3.3.4. Missing Data and Outliers**

Analysis visit windows will be applied as indicated in [Section 3.3.7](#). If an efficacy assessment is not available in an analysis visit window, then last observation carried forward (LOCF) will be applied to obtain a value for that analysis visit window for analyses conducted on the full analysis set population. For categorical efficacy endpoints, an additional sensitivity analysis will be conducted using non-responder imputation for cases where an efficacy assessment is not available in an analysis visit window. Missing data will not be imputed for safety summaries or efficacy summaries on the per protocol population.

There are multiple reasons that an assessment may not be available within an analysis visit windows:

- Clinic visits out of window or missed visits

- Data excluded from use in analysis due to confounding intercurrent event (see [Section 5.4.1.5](#))

For the latter reason, any assessments that occur after a confounding intercurrent event will be considered missing for purpose of analyses.

For analysis visit windows without an assessment, regardless of the reason, the last non-missing value prior to the start of the analysis visit window will replace the missing values. The baseline assessment can be carried forward.

If an AE has missing relationship to the study drug or severity, then that AE will be considered as ‘related’ to the study drug and the severity will be considered as ‘Severe’ in the table summaries, but the AE will be displayed as having a missing relationship or severity in the listings

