##### Logistic Analyses

For each treatment group, the observed achiever/responder rate for HiSCR50, [REDACTED], NRS30 and [REDACTED] will be reported along with the 90% CI for the response rate using the normal approximation. The difference in observed response rates will also be presented.

---

The percentage of patients achieving HiSCR50, [REDACTED], NRS30, and [REDACTED] at Week 12 and each scheduled analysis visit will be assessed using a Firth's penalized likelihood logistic regression model with fixed effect for treatment and an applicable baseline as a covariate. For HiSCR50, [REDACTED], and [REDACTED], the baseline covariate will be the count of inflammatory abscesses and nodules. For NRS30, the covariate will be the baseline PGA-SP. The analysis on the FAS population will use LOCF for missing values. An additional sensitivity analysis will be conducted for all of these responder endpoints except [REDACTED] where missing will be imputed as non-response.

Inferential results will include model-based responder estimates and associated 90% CIs, differences in estimates and associated 90% CIs for the active group versus placebo, and p-values testing for significance in the difference.

All efficacy data will be presented in data listings.

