Table 14.2.3 Percentage of Patients Achieving Hidradenitis Suppurativa Clinical Response [REDACTED] by Analysis Visit FAS Population, Missing Imputed as LOCF

Table 14.2.4 Percentage of Patients Achieving Hidradenitis Suppurativa Clinical Response [REDACTED] by Analysis Visit FAS Population, Missing Imputed as LOCF

Table 14.2.5.1 Percentage of Patients Achieving NRS30 among Patients with Baseline PGA of Skin Pain  $\geq 3$  by Analysis Visit, FAS Population, Missing Imputed as LOCF

Table 14.2.5.2 Percentage of Patients Achieving NRS30 among Patients with Baseline PGA of Skin Pain  $\geq 3$  by Analysis Visit, FAS Population, Missing Imputed as Non-Response

---

Table 14.2.5.3 Percentage of Patients Achieving NRS30 among Patients with Baseline PGA of Skin Pain  $\geq 3$  by Analysis Visit, PP Population

Table 14.2.6.1 Percentage of Patients Meeting █ Criteria by Analysis Visit, FAS Population, Missing Imputed as LOCF

Table 14.2.6.2 Percentage of Patients Meeting █ Criteria by Analysis Visit, FAS Population, Missing Imputed as Non-Response

Table 14.2.6.3 Percentage of Patients Meeting █ Criteria by Analysis Visit, PP Population

Table 14.2.7.1 Summary of IHS-4 Score and Change from Baseline by Analysis Visit, FAS Population

Table 14.2.7.2 Summary of IHS-4 Score and Change from Baseline by Analysis Visit, PP Population

Table 14.2.7.3 Analysis of Change from Baseline in IHS-4 by Analysis Visit, FAS Population

Table 14.2.7.4 Analysis of Change from Baseline in IHS-4 by Analysis Visit, PP Population

Table 14.2.8.1 Summary of HS-Physician's Global Assessment (HS-PGA) and Change from Baseline by Analysis Visit, FAS Population

Table 14.2.8.2 Summary of HS-Physician's Global Assessment (HS-PGA) and Change from Baseline by Analysis Visit, PP Population

Table 14.2.8.3 Analysis of Change from Baseline in HS-PGA by Analysis Visit, FAS Population

Table 14.2.8.4 Analysis of Change from Baseline in HS-PGA by Analysis Visit, PP Population

Table 14.2.9.1 Summary of DLQI Score and Change from Baseline by Analysis Visit, FAS Population

Table 14.2.9.2 Summary of DLQI Score and Change from Baseline by Analysis Visit, PP Population

Table 14.2.9.3 Analysis of Change from Baseline in DLQI Score by Analysis Visit, FAS Population

Table 14.2.9.4 Analysis of Change from Baseline in DLQI Score by Analysis Visit, PP Population

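### Read literally, the non-responder sensitivity analysis counts patients with missing data as not worsened on the lesion-count-increase endpoint

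*Protocol*

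**What the plan says.** Protocol 9.4.1, Table 5, sets out one method for a group of endpoints: "Treatment comparisons for all secondary responder endpoints". The group holds HiSCR, the 30% reduction in skin pain, and the "percentage of patients who experience at least a 25% increase in AN count with a minimum increase of 2 relative to Baseline". The synopsis gives the same list. On the first two endpoints, meeting the criterion is good; on the third it is bad.

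Protocol 9.4.4 sets the main rule for missing data: "All efficacy analyses conducted on the FAS population will use a LOCF analysis". It then adds that "a sensitivity analysis will be conducted for categorical endpoints conducted on the FAS using the non-responder imputation method", and leaves further detail to the SAP.

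SAP 3.3.4 says of categorical efficacy endpoints that "an additional sensitivity analysis will be conducted using non-responder imputation for cases where an efficacy assessment is not available in an analysis visit window". It names no exception. Under SAP 3.3.4 and 5.4.1.5, the unavailable assessments include everything after treatment discontinuation, a prohibited medication that could affect efficacy, or surgery.

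SAP 5.4.5 is more specific but partly blacked out: "An additional sensitivity analysis will be conducted for all of these responder endpoints except [REDACTED] where missing will be imputed as non-response". In the table list of SAP section 9, Table 14.2.6.2 is for an endpoint with a redacted name and is titled in part "Criteria by Analysis Visit, FAS Population, Missing Imputed as Non-Response".

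**The concern.** Non-responder imputation is conservative when response is the good outcome, because every patient without data counts as a failure. When the event is worsening, the same coding counts every patient without data as a success. An analysis meant to test the result against an unfavourable assumption then makes the favourable one.

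The SAP's rules on intercurrent events widen the effect. Protocol 7.1 prefers that patients who stop treatment keep attending visits, but their later counts are set to missing. A patient who worsens, stops treatment and is still worse at Week 12 would be recorded as not worsened. So would a patient who had already met the criterion at the last usable visit, whom LOCF would have kept as worsened.

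**Working it through.** **The plan's own figure.** The documents give no worsening rate and no missing-data rate, so this endpoint has no figure to reproduce. The one computed figure, 90.3% power, concerns the primary endpoint. With 45 per arm, a difference of 4.75 − 2.5 = 2.25, SD 3.6 and one-sided alpha 0.05, the noncentrality is 2.25 / (3.6 × √(2/45)) = 2.96. The t-test on 88 degrees of freedom then has power 90.27%, which agrees. It bears on this point only by confirming the arm size.

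**Inputs.** From the documents: 45 patients per arm, the endpoint definition and the imputation rule. Assumed: w, the proportion worsened among patients with data (15% to 35%); d, the proportion missing (10% to 30%); and m, the proportion worsened among patients with missing data.

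**Step 1, within one arm.**
- True rate: w(1 − d) + m·d
- Missing counted as not worsened: w(1 − d)
- Missing counted as worsened: w(1 − d) + d

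The literal rule understates the true rate by m·d. That is zero only if no missing patient worsened.

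**Step 2, against LOCF.** LOCF classes each missing patient as worsened or not. The literal rule classes all of them as not worsened. In each arm its worsening rate therefore cannot exceed the LOCF rate.

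**Step 3, between arms.** With the same w in both arms, the ATI-450 minus placebo difference is w(d_placebo − d_ATI) under the literal rule. If missing counts as worsened, it is that quantity plus (d_ATI − d_placebo). In percentage points, negative values favour ATI-450:

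| w | Missing, placebo vs ATI-450 | Missing = not worsened | Missing = worsened |
|---|---|---|---|
| 15% | 10% vs 20% | −1.5 | +8.5 |
| 15% | 10% vs 30% | −3.0 | +17.0 |
| 25% | 10% vs 20% | −2.5 | +7.5 |
| 25% | 10% vs 30% | −5.0 | +15.0 |
| 35% | 10% vs 20% | −3.5 | +6.5 |
| 35% | 10% vs 30% | −7.0 | +13.0 |
| 25% | 15% vs 15% | 0 | 0 |
| 25% | 20% vs 10% | +2.5 | −7.5 |

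At w = 25% and 10% versus 30% missing, the reported rates are 0.25 × 0.90 = 22.5% for placebo and 0.25 × 0.70 = 17.5% for ATI-450.

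**Step 4, effect on the test.** Suppose worsening is truly equal in the two arms. Rates of 22.5% and 17.5% with 45 per arm give about a 15% chance of one-sided p < 0.05 in favour of ATI-450, against a nominal 5%. At w = 35% the chance is about 18%. These come from a two-proportion normal approximation, not the Firth model of SAP 5.4.5.

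**Step 5, if missing patients worsen more often.** Take m = 60% and w = 25%. The true rates are 0.25 × 0.90 + 0.60 × 0.10 = 28.5% for placebo and 0.25 × 0.70 + 0.60 × 0.30 = 35.5% for ATI-450, which is 7 points worse. The literal rule still shows ATI-450 5 points better.

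**Step 6, which endpoint SAP 5.4.5 exempts.**
- Tables 14.2.3 and 14.2.4, the redacted HiSCR variants, have LOCF versions only.
- The 14.2.6 endpoint has LOCF, non-response and per-protocol versions.
- SAP 5.4.4 speaks of patients meeting this endpoint's criteria, but of patients achieving HiSCR50 and NRS30.
- SAP 5.4.5 uses baseline AN count as the covariate for HiSCR50 and both redacted entries, which fits an endpoint built on the AN count.

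So 14.2.6 is probably the worsening endpoint, and the exemption probably covers the HiSCR variants.

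**The case against.** The strongest reply is that the deciding text is hidden. Protocol 9.4.4 hands the detail to the SAP, SAP 5.4.5 does exempt something, and the endpoint's name, its definition and the list of changes from the protocol are redacted. The table list is also imperfect evidence: Tables 14.2.3 and 14.2.4 lack per-protocol versions too, although SAP 5.4 calls for both populations. This stands to the extent that the identification is an inference. It does not remove the need for an edit. If the exemption does cover worsening, SAP 3.3.4 still states the rule without it, and Table 14.2.6.2, if it carries that endpoint, contradicts SAP 5.4.5.

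A second reply is that non-responder imputation is commonly understood as counting missing patients as treatment failures, which here would mean worsened. That may be the intent, but SAP 5.4.5 imputes non-response and no readable text reverses the direction for this endpoint.

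Third, Table 5 describes worsening over the 12-week period. If that is cumulative, a patient who worsened before leaving may already count. But the same sentence calls for a separate analysis at each time point, and the SAP tables are by visit, so this is unresolved.

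Fourth, the opposite coding has its own artefact. Suppose 12 placebo and 6 ATI-450 patients are missing and 1 in 6 of those observed worsens. The literal rule gives 5.5/45 = 12.2% versus 6.5/45 = 14.4%. Counting missing as worsened gives 17.5/45 = 38.9% versus 12.5/45 = 27.8%, a gap of 11.1 points instead of 2.2. This stands, and it shapes the fix.

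A reader might also infer that the plan is tilted towards ATI-450, or that its main efficacy result is at risk. The documents support neither. The bias favours whichever arm has more missing data, which may be placebo, and the analysis concerned is secondary and supportive.

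**Conclusion.** The point holds as a defect in the stated rule. Protocol 9.4.4 and SAP 3.3.4, applied as written to an endpoint that Protocol Table 5 calls a responder endpoint, count missing patients as not worsened. That understates worsening in any arm where missing patients worsened, and cannot give a higher rate than LOCF.

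The between-arm bias needs unequal missingness. It is 1.5 to 7.0 points over the assumed ranges (w of 15% to 35%; 10% versus 20% or 30% missing) and zero when missingness and observed rates are equal. All these rates are assumptions.

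The reach is limited to one sensitivity analysis of a secondary endpoint, which does not appear in the visible part of Protocol Table 2. The LOCF analysis and the primary endpoint are unaffected. It cannot be said for certain that the SAP will produce the faulty table, because the exempted endpoint is redacted.

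**What to change.** In Protocol 9.4.4 and SAP 3.3.4 and 5.4.5, replace the general reference to non-responder imputation with a statement that the sensitivity analysis imputes the unfavourable outcome: non-achiever for HiSCR50 and NRS30, worsened for the AN-increase endpoint. Retitle Table 14.2.6.2 to match if it carries that endpoint.

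Present the result as a worst-case bound beside LOCF, and say in the SAP that it raises both arms' rates and penalises the arm with more missing data. If that bound is not wanted, exclude this endpoint from non-responder imputation by name in all three sections, and delete Table 14.2.6.2 if it carries the endpoint.

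The cost is a sentence in each place, one coding flag and a table title. No data collection or design changes. The price in reporting is a less favourable worsening rate in the sensitivity table.

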9.5 Interim Analyses

No interim analysis for efficacy is planned.

9.6 Data Monitoring Committee

An independent DSMB will convene to monitor interim safety data. The DSMB is responsible for reviewing and evaluating unblinded safety data at regularly scheduled meetings. The Committee may also meet in ad hoc meetings at its discretion as needed in response to events occurring in the study. Details regarding DSMB membership, responsibilities, and meeting frequency are outlined in the DSMB Charter.

## **GLOSSARY OF ABBREVIATIONS**

Abbreviation	Term
AE	Adverse Event
AESI	Adverse event of special interest
ALT	Alanine aminotransferase
AN	abscess and inflammatory nodule
Anti-CCP	Anti-cyclic citrullinated protein
AST	Aspartate aminotransferase
BID	Twice daily
BMI	Body mass index
BLQ	Below the limit of quantification
CI	Confidence Interval
CK	Creatine kinase
CTCAE	Common Terminology Criteria for Adverse Event
DLQI	Dermatology Quality of Life Index
DSMB	Data Safety Monitoring Board
ECG	Electrocardiogram
eCRF	Electronic case report form
EOS	End of Study
EOT	End of Treatment
ET	Early Termination
FAS	Full analysis set population
FSH	Follicle-stimulating hormone
HiCSR	Hidradenitis Suppurativa Clinical Response
HIV	Human immunodeficiency virus
HS	Hidradenitis suppurativa
HS-PGA	Physician Global Assessment Scale
hsCRP	High sensitivity C-reactive protein
ICH	International Council for Harmonisation
IHS-4	International Hidradenitis Suppurativa Severity Score System
IxRS	Interactive Voice/Web Response System
LOCF	Last observation carried forward
LS Means	Least squares mean
mRNA	Messenger RNA
MMRM	Mixed effect for repeated measures
PD	Pharmacodynamics
PE	Physical examination
PGA-SP	Patient's Global Assessment of Skin Pain
PK	Pharmacokinetics
PP	Per-protocol
PT	Preferred term
QTcF	Fridericia-corrected QT interval

RT-PCR	Reverse transcription polymerase chain reaction
SAE	Serious adverse event
SARS-CoV-2	Severe acute respiratory syndrome coronavirus 2
SI	Système International
SOC	System organ class
TE	Treatment emergent
TEAE	Treatment-emergent adverse event
TB	Tuberculosis
ULN	Upper limit of normal
WOCBP	Women of childbearing potential

